16.1.7. TUMOR SHRINKAGE

Tumor shrinkage will be estimated using data on sum of diameters of target lesion based on EAS. Percentage change in tumor size will be determined for patients with measurable disease at baseline and will be derived for each tumor assessment.

16.2. ANALYSIS OF EFFICACY VARIABLE(S)

The efficacy endpoints include ORR, DCR, DoR, PFS and OS. Efficacy data will be listed and summarized by dose cohort (only in dose escalation phase) or tumor specific cohorts (only in dose expansion phase) and disease type if applicable.

ORR, DCR, and DoR

The ORR and DCR will be summarized with percentages and 95% exact Clopper-Pearson confidence interval based on EAS.

DOR will be summarized using Kaplan-Meier method, and the descriptive statistics of median, 25% and 75% percentiles along with their 95% CIs will be calculated. It will be based on the EAS. The supportive data listings will also be provided.

PFS, OS, and Duration to Follow-Up

PFS and OS will be similarly summarized as DOR, and in addition to the quartile summary from Kaplan-Meier method, Kaplan-Meier estimates will be provided for the rates at 12, 16, 20, and 24 weeks along with their 95% CIs based on the Brookmeyer and Crowley method (1982).

In addition, duration (months) to follow-up for overall survival would be summarized by Kaplan-Meier method. Duration to follow-up refers to the time interval between date of first study drug administration and last date known to be alive for subjects who have not yet been reported to have died by the time of analysis, i.e. (date of last known to be alive – date of first study drug administration + 1)/ 30.475. Subjects who are reported to have died would be censored at death date.

Tumor Shrinkage

Document: [REDACTED]

Author: [REDACTED] Version Number: 2.5
Version Date: 18Feb2022

Template No.: [REDACTED] Reference: CS_WI_BS005

Effective Date: 02Dec2019

Percentage change in tumor size from baseline will be determined for patients with measurable disease at baseline and derived at each visit by the percentage change in the sum of the diameters of target lesions (TLs) compared to baseline. Best (minimum) percentage change from baseline (PCFB) in tumor size will be summarized using descriptive statistics and a waterfall plot will be presented also. Best post-baseline sum of diameter is defined as the sum of diameter with either the largest decrease or smallest increase from baseline sum of diameter at a single post-baseline evaluable tumor assessment visit before RECIST progression of disease. More details please refer to [section 16.1.7](#).

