## 8.5 Efficacy Analysis

The efficacy endpoints include PFS, ORR, DCR, and OS. Efficacy data will be listed and summarized by dose cohort and disease type.

The ORR and DCR will be summarized with percentages and 95% exact confidence intervals. The PFS rate at week 12 (Cohorts B and C) and week 16 (Cohorts D and E) and its 95% confidence intervals will be estimated by the Kaplan-Meier method. PFS, DoR, and OS will be summarized descriptively using Kaplan-Meier medians and quartiles. Percentage change in tumor size from baseline will be determined for patients with measurable disease at baseline and derived at each visit by the percentage change in the

sum of the diameters of target lesions (TLs) compared to baseline. Best percentage change in tumor size will be summarized using descriptive statistics and presented using a waterfall plot.

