### **Evaluation of Target Lesions**

**Complete Response (CR):** Disappearance of all target lesions. Any pathological lymph nodes (whether target or non-target) must have reduction in short axis to <10 mm.

**Partial Response (PR):** At least a 30% decrease in the sum of diameters of target lesions, taking as reference the baseline sum of diameters.

**Progressive Disease (PD):** At least a 20% increase in the sum of diameters of target lesions, taking as reference the smallest sum on study (this may include the baseline sum). The sum must also demonstrate an absolute increase of at least 5 mm.

**Stable Disease (SD):** Neither sufficient shrinkage to qualify for PR nor sufficient increase to qualify for PD.

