4.4. EFFICACY ANALYSIS SET [EAS]

This analysis set includes all patients who have received at least 1 dose of fruquintinib, have a measurable lesion (target lesions ≥ 10 mm) at the baseline tumor assessment, and either (i) have had at least one post-baseline tumor assessment, or (ii) do not have post-dose tumor assessment but have clinical progression as noted by the investigator, or have died due to disease progression before their first post-baseline tumor scan. All efficacy endpoints (i.e. BOR, ORR, DCR, DoR, and best percentage change from baseline in tumor size), not including PFS and OS, will be summarized based on this analysis set.

Document: [REDACTED]

Author: [REDACTED]

Version Number: 2.5

Version Date: 18Feb2022

Template No.: [REDACTED]

Reference: CS_WI_BS005

Effective Date: 02Dec2019

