16.1. PRIMARY EFFICACY VARIABLE(S) & DERIVATION(S)

16.1.1. BEST OVERALL RESPONSE (BOR)

BOR will be determined using time point responses (TPRs) up until the last evaluable TPR prior to or on the date of (i) disease progression as defined by RECIST Version 1.1 (Eisenhauer et al., 2009) or death; or (ii) withdrawal of consent; or (iii) receiving subsequent anti-cancer therapy, whichever is earlier.

The timing of an overall TPR will always be derived based on scan dates not response assessment dates. For a scheduled tumor scan assessment, it is expected that there may be a variation for the actual timing of scans among target, non-target, and new lesions. In assigning a date for the overall response assessment at a visit, the earliest date collected at that visit will be used. Within a grouped timepoint, if there are multiple assessments on different dates for the same target lesions, the last assessment will be used.

A patient's BOR will be determined based on [APPENDIX 3](#).

Document: [REDACTED]

Author: [REDACTED]

Version Number:

2.5

Version Date:

18Feb2022

Template No.: [REDACTED]

Reference: CS_WI_BS005

Effective Date: 02Dec2019

There are two ways of assigning BOR for a patient when the minimum interval for confirmation of CR and PR is not satisfied or if there are no confirmatory scans for CR and PR:

- Adding two more response categories as: unconfirmed CR, unconfirmed PR.
- Assigning BOR as SD, that is, both the unconfirmed CR and unconfirmed PR will be SD.

Both ways of assigning BOR will be implemented.

The number and percentage of patients in each category of derived BOR (Confirmed CR, Confirmed PR, SD, PD, or NE) will be summarized.

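### SAP 16.2 takes best tumor-size change only from visits before RECIST progression; read literally, first-scan progressors have no value and the waterfall plot loses its unfavorable end

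*SAP*

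**What the plan says.** Percentage change in tumor size is a secondary endpoint in both phases (Protocol 2.1.4 and 2.2.4; SAP 2.3.1 and 2.3.2).

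- **SAP 16.2, Tumor Shrinkage**, sets the output: "Best (minimum) percentage change from baseline (PCFB) in tumor size will be summarized using descriptive statistics and a waterfall plot will be presented also". The best sum is the one with the largest decrease or smallest increase from baseline, taken "at a single post-baseline evaluable tumor assessment visit before RECIST progression of disease".
- **SAP 16.1.1** sets a different window for best overall response (BOR): time point responses are used "up until the last evaluable TPR prior to or on the date of (i) disease progression as defined by RECIST Version 1.1", or up to death, withdrawal of consent or later anticancer therapy if earlier. SAP 16.1.5 uses the same inclusive form for PFS.
- **SAP 4.4** assigns the endpoint to the Efficacy Analysis Set (EAS): "best percentage change from baseline in tumor size), not including PFS and OS, will be summarized based on this analysis set". A treated patient with a measurable baseline lesion and one post-baseline tumor assessment is a member.
- **SAP 16.1.7** says that percentage change "will be derived for each tumor assessment".
- **Protocol 8.5** gives the same output without any limit at progression: "Best percentage change in tumor size will be summarized using descriptive statistics and presented using a waterfall plot". SAP 2.4, which lists changes from the protocol, does not mention one.

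**The concern.** The BOR and PFS rules count the progression date; the tumor-size rule stops short of it. A programmer who sets the three rules side by side has reason to apply the stricter filter here. A patient who progresses at the first post-baseline scan would then be PD in the BOR table and absent from the tumor-size summary and plot. No rule supplies a substitute value for such a patient, and none asks for a count of patients not shown.

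The patients lost this way are the earliest failures. The study has no control arm, and the primary objective of the expansion phase is anticancer activity. A waterfall plot without its immediate progressors would give too favorable a picture on that question. The loss would also differ between cohorts, because the first scan is at week 4 in Cohorts A and B and at week 8 in Cohorts C, D and E (Protocol 6.4).

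**Working it through.** The documents give no expected number for this summary, so there is no plan figure to reproduce. The check has three steps.

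**1. What the literal rule removes.** Protocol Appendix C defines target-lesion progression as "At least a 20% increase in the sum of diameters of target lesions, taking as reference the smallest sum on study", with an absolute rise of at least 5 mm. At the first post-baseline scan the smallest sum so far is the baseline sum, so target-lesion progression there means at least +20% and at least 5 mm from baseline. A patient kept under the literal rule has an earlier scan without progression, and the best change is a minimum over such scans. Every plotted value is therefore below +20%, apart from rises of less than 5 mm. The upper end is cut off by definition, whatever the data.

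**2. How many patients.** Assume exponential PFS, and take the two fruquintinib medians in metastatic colorectal cancer from Protocol 1.3.3: 3.71 months (Phase 3) and 4.731 months (Phase 2). The share with an event by day t is 1 − 0.5^(t / (median × 30.4375)). The planned size of Cohorts B and C is 40 each (Protocol 8.6).

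| Median (months) | First scan | Share with event | Of 40 |
|---|---|---|---|
| 3.71 | week 4 (28 days), Cohort B | 0.158 | 6.3 |
| 4.731 | week 4, Cohort B | 0.126 | 5.0 |
| 3.71 | week 8 (56 days), Cohort C | 0.291 | 11.6 |
| 4.731 | week 8, Cohort C | 0.236 | 9.4 |

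For example, 3.71 × 30.4375 = 112.9 days, and 1 − 0.5^(56/112.9) = 0.291.

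Given these medians, the counts are upper guides for two reasons. PFS events include deaths, and a patient who dies unscanned has no value under any rule. The denominator is planned enrollment, whereas the EAS requires a measurable lesion and inclusion criterion 7 also admits bone-only disease. For scale, Protocol Table 5 shows progression as best response in 6 of 34 evaluable patients (17.6%) in the Chinese Phase 1 study.

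**3. Effect on the mean, for illustration only.** Suppose first-scan change is normal with mean m and standard deviation s, and that only changes of +20% or more are dropped. With a = (20 − m)/s, the share dropped is 1 − Φ(a) and the mean of those kept is m − s·φ(a)/Φ(a).

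- m = 0, s = 20: a = 1; 16% dropped; kept mean = 0 − 20 × 0.242/0.841 = −5.8%, against 0% for all.
- m = 5, s = 25: a = 0.6; 27% dropped; kept mean = 5 − 25 × 0.333/0.726 = −6.5%, against +5% for all.

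The values of m and s are assumptions, chosen so that the dropped share is close to the range in step 2.

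**The case against.** The strongest reply is that the phrase was probably meant to bar scans taken after progression, because Protocol 3.6 allows treatment to continue beyond it. On that reading the progression scan counts and nothing is lost. The assignment to the EAS, the derivation at each assessment and the mention of a smallest increase can all be cited in support. The mock shells that fix the plot's content are not in these documents.

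This is plausible as intent, but no text states it. The EAS and per-assessment sentences conflict with the literal rule without overriding it. The mention of a smallest increase does not settle the matter, since stable-disease patients with growth under 20% would appear either way. What stands is that the wording is certain and the eventual output is not.

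Four further points hold in part:

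- The summary is descriptive, and SAP 5.5 plans no hypothesis tests. First-scan progressors still count as PD in BOR, as non-responders in ORR and as PFS events. This limits the consequence.
- Progression through new or non-target lesions can occur while target lesions are stable or shrinking. Dropping such a patient removes a favorable value, so the direction holds on average and not patient by patient.
- The protocol's silence carries little weight alone, because Protocol section 8 leaves analysis details to the SAP.
- The output groups in SAP Appendix 2 list only the escalation doses and Cohort A. The counts for Cohorts B and C assume that the 16.2 definition is applied to them, as its summary by tumor-specific cohort implies.

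**Conclusion.** The point holds as a defect in the stated definition. Followed literally, SAP 16.2 gives first-scan progressors no value, removes target-lesion growth of 20% or more from the plot, and biases the summary toward shrinkage on average. Under exponential PFS with medians of 3.71 to 4.73 months, about 13% to 16% of patients would have progressed or died by week 4 and 24% to 29% by week 8. That is at most about 5 to 6 of 40 in Cohort B and 9 to 12 of 40 in Cohort C. These figures assume that the earlier studies' medians carry over; Cohort B, with more prior therapy, may differ.

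A reader might infer more, in three ways that the documents do not support:

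- **That half of Cohort C would vanish.** The 1.84-month median in Protocol 1.3.3 would give 50% by week 8, or 20 of 40. It belongs to the placebo arm of the Phase 3 study, and every patient here receives fruquintinib.
- **That the SAP says these patients are excluded.** It does not; the omission follows from the definition.
- **That the efficacy results as a whole are inflated.** ORR, DCR, PFS and OS do not use this rule.

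The correction should be made before the outputs are produced, but the primary analysis does not depend on it.

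**What to change.** In SAP 16.2, replace the restriction to visits before progression with the BOR window of 16.1.1, for example: *at a single evaluable post-baseline assessment within the window of Section 16.1.1, including the assessment that documents first RECIST progression*. That window closes at the earliest of first RECIST progression or death, withdrawal of consent, and subsequent anticancer therapy, and counts assessments on the closing date. Apply it to both the descriptive summary and the waterfall plot.

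Tie the program filter to the assessment visit rather than to a single calendar date. SAP 16.1.1 allows scans within a visit to fall on different days and dates the overall response by the earliest, so a date filter could still lose the target-lesion sum.

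Footnote the number of EAS patients with no evaluable post-baseline sum. This will include those who enter the EAS under 4.4 through clinical progression or death from disease before any scan. Section 16.1.7 needs only a cross-reference.

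The cost is one phrase, the matching program filter and a footnote. No new data are needed. The plot may look less favorable. If inclusion was always intended, the edit only removes the ambiguity.

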17. SAFETY OUTCOMES

Unless otherwise specified, the overall safety evaluation period is from the first date of study drug administration to no later than 37 days after the date of last study treatment administration. All outputs for safety outcomes will be based on the SAS.

There will be no statistical comparisons between the treatment groups for safety data, unless otherwise specified with the relevant section.

Safety will be assessed through summaries of adverse events, changes in laboratory test results, changes in vital signs and change in ECG. Safety data will be listed and summarized. Incidence of DLTs will be listed by dose cohort for dose escalation phase only.

17.1. DLTs

A DLT is defined as one of the following toxicities occurring during the DLT assessment window (Cycle 1) and determined by the investigator to have a reasonable possibility of being related to fruquintinib. All DLT analysis will be performed for dose escalation phase only. In addition to summarizing the proportion of patients with DLTs, the DLT categories will also be summarized as follows:

- Any Grade 4 non-hematologic toxicity;
- Any Grade 3 non-hematologic toxicity related to study drug except for nausea/vomiting, diarrhea, constipation, hypertension and electrolyte imbalances downgraded within 3 days with appropriate supportive treatment;
- Grade 4 neutropenia lasting > 3 days;
- Grade 3 febrile neutropenia (absolute neutrophil count < 1.0 x 10⁹/L with a single temperature of > 38.3 °C or a sustained temperature of ≥38 °C for more than 1 hour);
- Grade 4 thrombocytopenia or Grade 3 thrombocytopenia associated with bleeding;
- DLT leading to dose interruption for > 14 days due to toxicity

The individual data of DLTs will also be listed by dose and/ or disease cohort and by patient.

Document: [REDACTED]

Author: [REDACTED] Version Number: 2.5
Version Date: 18Feb2022

Template No.: [REDACTED] Reference: CS_WI_BS005

Effective Date: 02Dec2019

17.2. ADVERSE EVENTS

AEs will be coded using Medical Dictionary for Drug Regulatory Activities (MedDRA) central coding dictionary, Version 23.1 or higher.

Treatment emergent adverse events (TEAEs) are defined as AEs that started or worsened in severity on or after the first dose of study medication and no later than 37 days after the date of last study treatment. In case that the AE onset date coincide with the first dose date of study treatment, AE will be considered as TEAE if the response of question “Did the adverse event occur prior to the start of study treatment?” in AE form is “No”.

See [section 6.3.2](#) for handling of partial dates for AEs. In the case where it is not possible to define an AE as treatment emergent or not, (i.e., the required imputed dates are missing or partial) the AE will be classified by the worst case, i.e. treatment emergent.

An overall summary of number of patients within each of the categories described in the sub-section below, will be provided.

Listings will include all the AEs being reported during the study with flag to distinguish TEAEs and Non-TEAEs. Imputed AE dates will not be presented in the listings.

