### 7.1.4 Adverse Events Reporting Period

After informed consent, but prior to initiation of study drug, all SAEs regardless of attribution will be collected.

After initiation of study drug, all AEs and SAEs, regardless of attribution will be collected until 30 days following the last dose of study drug or a new treatment of anti-tumor therapy, whichever is earlier. After this period, investigators should report only SAEs that are

considered to be related to the study drug.

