### 8.3 Safety Analysis

Safety will be assessed through AEs, laboratory assessments, vital signs, and ECG results. Safety data will be listed and summarized by dose cohort across the 2 phases. All DLT events will be listed by dose cohort for the dose escalation phase only.

Severity of AEs will be graded by the investigator according to NCI CTCAE v4.03. If a CTCAE criterion does not exist, the grade corresponding to the appropriate adjective will be used by the investigator to describe the maximum intensity of the adverse event: Grade 1 (mild), Grade 2 (moderate), Grade 3 (severe), Grade 4 (life threatening), or Grade 5 (fatal) (see Section 7.1.6). All AEs will be coded with Medical Dictionary for Drug Regulatory Activities (MedDRA).

All AEs will be listed. The focus of safety data summarization will be on treatment-emergent adverse events (TEAEs), which are defined as AEs that occur or worsen in the period extending from the first dose of study drug to 30 days after the last dose of study drug in this study.

TEAEs will be summarized as the number of patients and corresponding percentage by MedDRA System Organ Class (SOC) as well as Preferred Term (PT). The incidence of TEAEs, SAEs, adverse events of special interest (AESIs), AEs leading to dose interruption, reduction, or treatment discontinuation will be presented by SOC and PT; by relationship to the investigational product and by toxicity grade for each dose level. Changes in laboratory data will be summarized by severity grade using the NCI CTCAE v4.03. When abnormal laboratory results at the patient level are counted, the worst value during study treatment will be chosen.

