17.3. DEATHS

Data on death will be listed, along with results of total number of patients died and cause of death summarized. Result of patients with on-study death, which is defined as the death after the first dose until 37 days after last dose, will also be tabulated. On-treatment death will be flagged.

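### SAP 17.2 counts TEAEs to 37 days after last dose where protocol 8.3 stops at 30; the change is undeclared, and new events in the added week are only selectively reported

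*SAP*

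**What the plan says.** - **SAP 17.2** lets a TEAE start or worsen "no later than 37 days after the date of last study treatment". **SAP 17** sets the same default end for the overall safety period: "no later than 37 days after the date of last study treatment administration".
- **Protocol 8.3** defines the TEAE period as "from the first dose of study drug to 30 days after the last dose of study drug in this study".
- **Protocol 7.1.4** sets what sites must report. Once treatment has begun, "all AEs and SAEs, regardless of attribution will be collected until 30 days following the last dose of study drug"; the period closes sooner if the patient begins another cancer treatment first. Beyond that point only serious events judged related to study drug are to be reported. Protocol Appendix A footnote 16 gives the same rule, and SAP Appendix 1 reproduces that footnote.
- **SAP 2.2** also describes safety monitoring in the expansion phase as ending 30 days after the last dose.
- **SAP 2.4** lists the departures from the protocol: the efficacy set, the set used for PFS and OS, subsequent oncology therapy, and the inequality signs in the Hy's Law and liver-injury criteria. It does not list the TEAE window.
- **SAP 17.3** separately takes an on-study death to be "the death after the first dose until 37 days after last dose".

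**The concern.** The analysis window is longer than the period in which sites must report everything. A TEAE table is normally read on the footing that all adverse events in its window were sought. For new events in the last 7 days of the SAP window that is not so: the reporting rule admits an event only if it is both serious and related.

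Every table built on the SAP 17.2 definition inherits this: all TEAEs, related TEAEs, grade 3 or higher, serious, leading to discontinuation, leading to death, and events of special interest. The counts then differ from those the protocol's definition would give, and the late additions lean towards serious and related events. Because SAP 2.4 is silent, a reader of the report would not know that the definition had changed.

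**Working it through.** No sample-size, power or alpha figure is involved. The check sets the two windows against the reporting rule.

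**1. Window lengths.** SAP 37 days, protocol 30 days: 37 − 30 = 7 days. Relative to the protocol's post-dose period, 7 / 30 = 23%.

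**2. What is counted and what must be reported for a new-onset event.**

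| Time after last dose | TEAE under protocol 8.3 | TEAE under SAP 17.2 | Must be reported (protocol 7.1.4) |
|---|---|---|---|
| To day 30, no new anti-tumor therapy | yes | yes | all AEs and SAEs |
| To day 30, after new anti-tumor therapy | yes | yes | related SAEs only |
| Days 31 to 37 | no | yes | related SAEs only |
| After day 37 | no | no | related SAEs only |

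The third row is the one the SAP adds.

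**3. Patients who start new therapy early.** If new anti-tumor therapy starts on day d < 30 after the last dose, the part of each window without full reporting is:
- SAP: 37 − d days
- Protocol: 30 − d days

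With d = 14 (an assumed value), this is 37 − 14 = 23 days and 30 − 14 = 16 days. The SAP always adds 7 days. The remaining gap is already present in the protocol's own definition, because protocol 8.3 does not mention new therapy.

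**4. Direction.** The 30-day window lies inside the 37-day window and the denominator is the same safety set. A 37-day patient count therefore cannot be lower than the 30-day count. A new event captured under the late reporting rule is by construction serious and related, so it adds to those rows.

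**5. Size per patient.** One extra patient in a table row is 1/15 = 6.7 percentage points in Cohort D or E and 1/40 = 2.5 points in Cohort B or C. The documents give no event rate for days 31 to 37, so an expected number cannot be derived.

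**6. Likely origin of 37 days (an inference).** 30 + 7 = 37 matches the upper limit of the Treatment Completion visit window. However, protocol 6.5 and Appendix A footnote 3 time that visit from the decision to stop treatment permanently, not from the last dose. It need not fall on or before day 37 after the last dose.

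**The case against.** **The added week is not confined to related serious events.** This stands. SAP 17.2 also counts events that worsen, protocol 6.5 and 7.3 follow ongoing events, and protocol 7.1.8.3 updates the severity of a persistent event when it rises. The schedule of events also marks adverse events at the Treatment Completion visit. A reader might infer from the reporting rule that days 31 to 37 hold nothing but related serious events; the documents do not support that. Capture of other events there depends on the patient and the visit date, so it is partial.

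**On-study deaths.** A reader might infer that the 37-day death window in SAP 17.3 has the same fault. It does not. The protocol uses the term in 7.1.8.5 without a 30-day limit. Protocol 3.1.1 and 3.1.2 follow patients through to death or the end of the study, and Appendix A footnote 17 records date and cause of death in survival follow-up for Cohorts B to E. The 30-day period decides whether a death is reported as an adverse event, not whether it is recorded.

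**New anti-tumor therapy.** A reader might infer that the longer window is what brings in events after new therapy, or that it attributes them to fruquintinib. Protocol 8.3 has no such cut-off either, so the issue exists at 30 days too, and being a TEAE is not a statement of cause, which the investigator assesses. What stands is that neither definition says how these events are treated.

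**Consequence.** Safety output is descriptive, with no hypothesis tests (SAP 5.5) and no comparisons between groups (SAP 17). A longer window cannot hide a signal. All events are listed with dates and a TEAE flag, so 30-day counts can be rebuilt. A patient who already has the same term adds nothing to that row. This limits the importance of the point, but the summary tables would still carry an undeclared definition. Using 37 days consistently across the SAP explains the choice but does not extend adverse-event reporting.

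**Conclusion.** The discrepancy is real for TEAEs: 37 days in SAP 17.2 against 30 in protocol 8.3, not listed in SAP 2.4, and at odds with the 30-day reporting rule that the SAP itself reproduces. New events in the added 7 days are incompletely and selectively observed and can only raise TEAE counts, mainly serious and related ones.

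The effect is probably small. That few events are expected is a judgement, since the documents give no rate. The 6.7-point figure shows what one patient weighs in a 15-patient cohort; it is not a predicted bias. The conclusion assumes that sites follow protocol 7.1.4 as written. If they routinely record all new events at a late Treatment Completion visit, the selection is weaker but the undeclared difference remains.

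**What to change.** 1. In SAP 17.2, end the TEAE window 30 days after the last dose, as in protocol 8.3. SAP 17 allows exceptions to its default period, so that sentence can stay.
2. List related serious events with later onset separately, so nothing reported is lost.
3. State how events that start after new anti-tumor therapy are handled. Full reporting ends there under protocol 7.1.4, while protocol 8.3 is silent. Either choice should be written down as a SAP rule, not presented as already in 8.3.
4. Keep 37 days for laboratory, ECG and vital-sign data (SAP 17.4 to 17.6). Leave the on-study death definition in SAP 17.3 as it is.

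If the sponsor prefers 37 days for TEAEs, declare it in SAP 2.4 with a note on the limited reporting after day 30, and show the 30-day counts as well.

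The cost is a few lines of SAP text, one programming constant and one short listing. No new data are needed.
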